11.9 Appendix 9: Liver Safety

Phase III-IV liver chemistry stopping and follow-up criteria have been designed to assure patient safety and evaluate liver event etiology (in alignment with the FDA premarketing clinical liver safety guidance). Phase III-IV liver chemistry stopping criteria 1-5 are defined below. Investigators may at their discretion refer patients meeting liver safety criteria below to a specialist who may determine the appropriate or medically necessary additional or confirmatory laboratory tests or procedures as required by the protocol or otherwise deemed necessary (e.g. liver imaging).

1. ALT \geq 3xULN and bilirubin \geq 2xULN (35% direct bilirubin) (or ALT \geq 3xULN and INR $>$ 1.5, if INR measured).

Note: if serum bilirubin fractionation is not immediately available, withdraw study drug for that patient if ALT \geq 3xULN and bilirubin \geq 2xULN. Serum bilirubin fractionation should be performed if testing is available. If testing is unavailable, record presence of detectable urinary bilirubin on dipstick, indicating direct bilirubin elevations and suggesting liver injury.

2. ALT \geq 8xULN.
3. ALT \geq 5xULN but $<$ 8 xULN persists for \geq 2 weeks.
4. ALT \geq 3xULN if associated with symptoms (new or worsening) believed to be related to hepatitis (such as fatigue, nausea, vomiting, right upper quadrant pain or tenderness, or jaundice) or hypersensitivity (such as fever, rash or eosinophilia).
5. ALT \geq 5xULN but $<$ 8 xULN and cannot be monitored weekly for \geq 2 weeks.

When any of the liver stopping criteria 1-5 is met do the following:

- **Immediately** discontinue blinded study medication/investigational product for that patient.
- Report the event to IQVIA within 24 hours of learning its occurrence.
- Complete the liver event CRF and SAE data collection tool if the event also meets the criteria for an SAE. All events of ALT \geq 3xULN and bilirubin \geq 2xULN (35% direct bilirubin) (or ALT \geq 3xULN and INR $>$ 1.5, if INR measured); INR measurement is not required and the threshold value stated will not apply to patients receiving anticoagulants), termed 'Hy's Law' must be reported as an SAE (excluding studies of hepatic impairment or cirrhosis).

Note: if serum bilirubin fractionation is not immediately available, discontinue blinded study medication/investigational product for that patient if ALT \geq 3xULN and bilirubin \geq 2xULN. Serum bilirubin fractionation should be performed if testing is available. If testing is unavailable, record presence of detectable urinary bilirubin on dipstick, indicating direct bilirubin elevations and suggesting liver injury.

- Complete the liver imaging and/or liver biopsy CRFs if these tests are performed.
- Perform liver event follow-up assessments and monitor the patient until liver chemistries resolve, stabilize, or return to baseline values as described below.
- Discontinue blinded study medication/investigational product after completion of the liver chemistry monitoring as described below.
- Do not restart investigational product.

In addition, for criterion 1:

- Make every reasonable attempt to have patients return to clinic within 24 hours for repeat liver chemistries, liver event follow-up assessments (see below), and close monitoring.
- A specialist or hepatology consultation is recommended.
- Monitor patients twice weekly until liver chemistries (ALT, AST, alkaline phosphatase, bilirubin) resolve, stabilize or return to within baseline values.

For criteria 2, 3, 4, and 5:

- Make every reasonable attempt to have patients return to clinic within 24-72 hours for repeat liver chemistries and liver event follow-up assessments (see below).
- Monitor patients weekly until liver chemistries (ALT, AST, alkaline phosphatase, bilirubin) resolve, stabilize, or return to within baseline values; criterion 5 patients should be monitored as frequently as possible.

Patients with ALT $\geq 5xULN$ and $< 8xULN$ which exhibit a decrease to ALT $\geq 3xULN$, but $< 5xULN$ and bilirubin $< 2xULN$ without hepatitis symptoms or rash, and who can be monitored for 4 weeks:

- Notify the IQVIA Medical Monitor within 24 hours of learning of the abnormality to discuss patient safety.
- Can continue investigational product
- Must return weekly for repeat liver chemistries (ALT, AST, alkaline phosphatase, bilirubin) until they resolve, stabilize or return to within baseline.
- If at any time these patients meet the liver chemistry stopping criteria, proceed as described above.
- If, after 4 weeks of monitoring, ALT $< 3xULN$ and bilirubin $< 2xULN$, monitor patients twice monthly until live chemistries normalize or return to within baseline values.

For criteria 1-5, make every attempt to carry out the liver event follow up assessments described below:

- Viral hepatitis serology including
 - Hepatitis A IgM antibody
 - Hepatitis B surface antigen and Hepatitis B Core antibody (IgM)
 - Hepatitis C RNA
 - Cytomegalovirus IgM antibody
 - Epstein-Barr viral capsid antigen IgM antibody (or if unavailable, obtain heterophile antibody or monospot testing).
 - Hepatitis E IgM antibody
- Blood sample for PK analysis, obtained within 72 hours of the last dose. Record the date/time of the PK blood sample draw and the date/time of the last dose of blinded study medication/investigational product prior to blood sample draw on the CRF. If the date or time of the last dose is unclear, provide the patient's best approximation. If the date/time of the last dose cannot be approximated OR a PK sample cannot be collected in the time period indicated above, do not obtain a PK sample. Instructions for sample handling and shipping are in the SPM.
- Serum creatinine phosphokinase (CPK) and lactate dehydrogenase (LDH)
- Fractionate bilirubin, if total bilirubin $\geq 2xULN$
- Obtain complete blood count with differential to assess eosinophilia.
- Record the appearance or worsening of clinical symptoms of hepatitis or hypersensitivity such as fatigue, nausea, vomiting, right upper quadrant pain or tenderness, fever, rash or eosinophilia as relevant on the AE report form.
- Record use of concomitant medications, acetaminophen, herbal remedies, or over the counter medications, or putative hepatotoxins, on the concomitant medications report form.
- Record alcohol use on the liver event alcohol intake case report form.

The following are required for patients with ALT $\geq 3xULN$ and bilirubin $\geq 2xULN$ (35% direct) but are optional for the other abnormal liver chemistries:

- Anti-nuclear antibody, anti-smooth muscle antibody, and Type 1 anti-liver kidney microsomal antibodies and quantitative total immunoglobulin G (IgG or gamma globulins).

- Serum acetaminophen adduct HPLC assay (quantifies potential acetaminophen contribution to liver injury in patients with definite or likely acetaminophen use in the preceding week [James, 2009]. NOTE: not required in China.
- Only in those with underlying chronic hepatitis B at study entry (identified by positive hepatitis B surface antigen): quantitative hepatitis B DNA and hepatitis delta antibody. NOTE: if hepatitis delta antibody assay cannot be performed, it can be replaced with a PCR of hepatitis D RNA virus where needed (Le Gal, 2005).

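### Appendix 9 tells sites both to stop study medication at once and to stop it after liver monitoring ends, and Section 7.1.2 does not say which applies

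*Protocol*

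**What the plan says.** Protocol Section 11.9 defines five liver chemistry stopping criteria and then opens a single action list: "When any of the liver stopping criteria 1-5 is met do the following". The first bullet, with the word immediately in bold, tells the site to "discontinue blinded study medication/investigational product for that patient". Further down the same list come three bullets in a row:

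- The first of the three covers monitoring: "Perform liver event follow-up assessments and monitor the patient until liver chemistries resolve, stabilize, or return to baseline values as described below"
- The second is another stop instruction, with a different time: "Discontinue blinded study medication/investigational product after completion of the liver chemistry monitoring as described below"
- The third rules out giving the drug again: "Do not restart investigational product"

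A note on bilirubin fractionation appears twice. Under criterion 1 it reads "if serum bilirubin fractionation is not immediately available, withdraw study drug for that patient". Inside the action list it reads "if serum bilirubin fractionation is not immediately available, discontinue blinded study medication/investigational product for that patient". Both versions apply when ALT is at least 3xULN and bilirubin at least 2xULN.

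Protocol Section 7.1.2, the body-text section on liver stopping, refers to Section 11.9. It says only that the Investigator should consider discontinuation when one of the conditions there is met, or when stopping is judged best for the patient.

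**The concern.** The first bullet and the deferred-stop bullet concern the same patients and the same product but give incompatible times for the last dose. Followed literally, the deferred bullet would keep a patient with, for example, ALT of 8xULN or more on drug until the liver tests had settled. The body text does not break the tie, and its softer wording could let a site treat the stop as optional.

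What is at stake is patient safety and consistency between sites. Two features of the study add some weight. There is no data monitoring committee (SAP Section 4.1), so the site-level rule carries more of the protection. Chronic stable hepatitis B or C does not exclude a patient (Protocol Section 5.2, criterion 12, and Section 8.1.10.1), so some patients may enter with underlying liver disease.

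**Working it through.** No formula applies, because the point depends on no rate, variance or error probability. The check is a comparison of the current text, followed by a count.

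**Is it one list?** Yes. The second bilirubin note falls between the opening bullets and the later ones but does not start a new list. The bullets run on until the extra instructions for criterion 1 begin.

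**Does the deferred bullet belong to another group?** No. Patients whose ALT falls from 5 to <8xULN down to 3 to <5xULN may continue on drug, but they are covered in a separate, later block. That block sends them back to the action list if they meet a stopping criterion.

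**Could it mean leaving the study rather than stopping drug?** It does not say so. Sections 7.1 and 7.2 state that stopping medication does not require withdrawal from the study, except for active COVID-19.

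**When would the deferred stop occur?** Three monitoring bullets apply to patients meeting criteria 1 to 5: the general one quoted above, a twice-weekly one for criterion 1 ("Monitor patients twice weekly until liver chemistries (ALT, AST, alkaline phosphatase, bilirubin) resolve, stabilize or return to within baseline values"), and a weekly one with the same end condition for criteria 2 to 5. Bullets that set a maximum duration: 0 of 3.

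**Count of stop instructions in Section 11.9:**

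| Patients | Stop at once | Stop after monitoring |
|---|---|---|
| Criterion 1 | 1 bullet + 2 notes = 3 (the notes apply only if fractionation is not immediately available) | 1 |
| Criteria 2 to 5 | 1 bullet | 1 |

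The two notes describe the ALT-with-bilirubin pattern of criterion 1. For criteria 2 to 5 the first bullet is therefore the only explicit instruction to stop at once.

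**Does Section 7.1.2 decide it?** No. It gives no timing. Section 7.1.5 (pregnancy) and Section 7.1.6 (active COVID-19) show that the protocol uses mandatory wording where a stop is compulsory; Section 7.1.2 does not.

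**Which reading was intended?** The emphasis on the first bullet, both notes and the ban on restarting all point to an immediate, permanent stop. This is inference, since no sentence gives either bullet precedence.

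**The case against.** The strongest reply is that Appendix 9, read as a whole, has only one workable meaning, and that a count of bullets understates this for criteria 2 to 5. All five are called stopping criteria. Criterion 5 applies precisely because the patient cannot be monitored weekly, so a stop deferred until monitoring ends makes no sense there. Criterion 3 is met only after at least two weeks of raised ALT. A PK sample is due within 72 hours of the last dose, which fits dosing that has already ended. Permission to continue is written as an exception for the falling-ALT group. All of this stands, but it confirms the intended rule without removing the contrary instruction.

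Section 7.1 also uses discretionary wording elsewhere, for ECG findings (7.1.3) and other reasons (7.1.7), so Section 7.1.2 is not unusual. That is fair. Even so, Section 7.1.2 cannot settle the timing, and its wording is weaker than the command in the appendix it refers to.

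Practical reach may also be small. As extracted, the schedule in Section 1.3 appears to place routine post-baseline chemistry only at Week 24 and early termination, although the column alignment is unreliable. If so, mid-treatment triggers would come mainly from unscheduled tests, when the investigator is already alert. Section 11.9 also requires a report within 24 hours, and Section 8.0 requires immediate discussion of safety concerns with the Sponsor. These points limit the weight of the finding but do not remove it.

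Finally, the COVID-19 clarification letters explained a term, which makes them weak precedent for turning a recommendation into an obligation. That bears on the route for the Section 7.1.2 edit, not on the need for it.

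**Conclusion.** The concern holds. The current text of Section 11.9 contains two incompatible stop instructions for the same patients, and neither the appendix nor Section 7.1.2 says which governs. It is a drafting error in an operative safety rule and should be corrected.

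Its size is modest. The documents give no rate of liver events and no maximum monitoring time, so no count of added doses or affected patients can be given. There is no material effect on the primary analysis, which follows a treatment policy strategy (SAP Section 2.5). The gain is one unambiguous rule. The conclusion assumes that an immediate stop was intended, which the surrounding text strongly supports.

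**What to change.** 1. In Section 11.9, delete the deferred-stop bullet. The bullet directly above it already requires monitoring to continue, so no follow-up is lost.
2. In Section 7.1.2, write: *Blinded study medication must be discontinued immediately when any of stopping criteria 1-5 in Section 11.9 is met; for other liver abnormalities it may be discontinued at the Investigator's discretion.*
3. Leave unchanged the permission to continue for the falling-ALT group, and the weekly observation of ALT from 5 to <8xULN that criteria 3 and 5 imply before a criterion is met.

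The cost is one deleted bullet and one reworded sentence, with no change to visits, data collection or analysis. A protocol clarification letter is proportionate for telling sites that the immediate stop governs; SAP Section 17.5 shows that such letters have been used for the COVID-19 withdrawal rule. Both edits should then enter the next amendment. Under Section 11.2 that needs IRB/IEC approval and, when applicable, regulatory approval, across about 151 centers.

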11.10 Appendix 10: Medical Device Information

Definitions of a Medical Device Incident

The detection and documentation procedures described in this protocol apply to all Sponsor medical devices provided for use in the study (see Section 6.2.2) for the list of Sponsor medical devices).

Medical Device Incident Definition

- A medical device incident is any malfunction or deterioration in the characteristics and/or performance of a device as well as any inadequacy in the labeling or the instructions for use which, directly or indirectly, might lead to or might have led to the death of a patient/user/other person or to a serious deterioration in his/her state of health.
- Not all incidents lead to death or serious deterioration in health. The nonoccurrence of such a result might have been due to other fortunate circumstances or to the intervention of health care personnel.

It is sufficient that:

- An incident associated with a device happened.

AND

- The incident was such that, if it occurred again, might lead to death or a serious deterioration in health.

A serious deterioration in state of health can include any of the following:

- Life-threatening illness.
- Permanent impairment of body function or permanent damage to body structure.
- Condition necessitating medical or surgical intervention to prevent 1 of the above.
- Fetal distress, fetal death, or any congenital abnormality or birth defects.

Examples of Incidents

- A patient, user, caregiver, or healthcare professional is injured as a result of a medical device failure or its misuse.
- A patient's blinded study medication is interrupted or compromised by a medical device failure.
- A misdiagnosis due to medical device failure leads to inappropriate treatment.
- A patient's health deteriorates due to medical device failure.

Documenting Medical Device Incidents***Medical Device Incident Documenting***

- Any medical device incident occurring during the study will be documented in the patient's medical records, in accordance with the Investigator's normal clinical practice, and on the appropriate form of the CRF.
- For incidents fulfilling the definition of an AE or an SAE, the appropriate AE/SAE CRF page will be completed as described in Section 11.7.
- The CRF will be completed as thoroughly as possible and signed by the Investigator before transmittal to the Sponsor or designee.
- It is very important that the Investigator provides his/her assessment of causality (relationship to the medical device provided by the Sponsor) at the time of the initial AE or SAE report and describes any corrective or remedial actions taken to prevent recurrence of the incident.
- A remedial action is any action other than routine maintenance or servicing of a medical device where such action is necessary to prevent recurrence of an incident. This includes any amendment to the device design to prevent recurrence.

11.11 Appendix 11: Country Specific Requirements

Germany: a CXR or CT scan must be available in the 12 months prior to Screening for eligibility.

1. INTRODUCTION

This document describes the rules and conventions to be used in the presentation and analysis of efficacy and safety data, including genotyping data for Protocol RPL554-CO-302. It describes the data to be summarized and analyzed, including specifics of the statistical analyses to be performed.

This statistical analysis plan (SAP) is based on protocol version 5.0, dated 30th April 2021.

A separate analysis plan will be created which will include the details of the population PK (POPPK) analysis, as well as the design and modelling of the PK collection data. Only summarization of PK concentrations will be described in this SAP.

A separate pooled SAP will be created which will include the details of pooled analysis between RPL554-CO-301 and RPL554-CO-302.

There will also be a separate blinded data review (BDR) plan that will outline the process for identification and decision making on patient's exclusion from analysis sets and on major protocol deviations specified in the BDR plan. These will then be summarized in BDR report created for the data review outputs. This document will summarize each analysis set and reasons for the exclusion. In the BDR report protocol deviations (PDs) will also be outlined, specifying which patients were identified with each PD and whether these led to exclusion from the PP population. All analysis sets will be defined, and all possible PDs will be identified prior to unblinding. If there are any PDs which can only be identified post-unblinding (e.g. in PK or Biomarker data), an unblinded data review report will be created to detail these after database lock (DBL).

2. STUDY OBJECTIVES AND ESTIMANDS

2.1. PRIMARY OBJECTIVE

The primary objective of this study is to evaluate the efficacy of ensifentrine on lung function compared to placebo over a 12-hour dosing interval in patients with moderate to severe chronic obstructive pulmonary disease (COPD).

2.2. SECONDARY OBJECTIVES

- To evaluate the effect of ensifentrine on other lung function parameters.
- To evaluate the effect of ensifentrine on COPD symptoms.
- To evaluate the effect of ensifentrine on health-related quality of life.

2.3. OTHER OBJECTIVES

- To evaluate the effect of ensifentrine on moderate/severe COPD exacerbations.
- To evaluate the effect of ensifentrine on health utility and healthcare resource utilization (HRU).
- To characterize the pharmacokinetics of ensifentrine in patients with COPD.
- To evaluate the effect of ensifentrine on inflammatory biomarkers.

2.4. SAFETY OBJECTIVES

To evaluate the safety and tolerability of ensifentrine over 24 Weeks.

2.5. ESTIMANDS

The primary and secondary estimands to support regulatory decisions are described in Table 1.

Table 1: List of Estimands

		Attributes			
Estimand	Definition	Population	Variable/ Endpoint	Intercurrent event handling strategy	Population-level summary measure
Primary	The efficacy of ensifentrine on lung function compared to placebo over a 12-hour dosing interval in patients with moderate to severe COPD.	Patients with moderate to severe COPD aged 40-80 years (inclusive) that are in the modified intent-to-treat (mITT) population. See full list of inclusion and exclusion criteria in sections 5.1, 5.2 and 5.3 of study protocol.	Change from baseline forced expiratory volume in 1 second (FEV ₁) to average FEV ₁ area under the curve over 12 hours (AUC _{0-12h}) at Week 12.	Regardless of whether the patient discontinues treatment prematurely and regardless of major protocol deviation, as per the Treatment Policy strategy.	Estimated treatment difference at Week 12 of the double-blind period (and corresponding 95% confidence interval [CI]) from analysis of covariance (ANCOVA) analysis.
Secondary	To evaluate the effect of ensifentrine on other lung function parameters.	Patients with moderate to severe COPD aged 40-80 years (inclusive) that are in the mITT population. See full list of inclusion and exclusion criteria in sections 5.1, 5.2 and 5.3 of study protocol.	
 Change from baseline FEV₁ to average FEV₁ AUC_{0-4h} at Week 12 Change from baseline FEV₁ to peak FEV₁ at Week 12 Change from baseline FEV₁ to morning trough FEV₁ at Week 12 	Regardless of whether the patient discontinues treatment prematurely and regardless of major protocol deviation, as per the Treatment Policy strategy.	Estimated treatment difference at Week 12 of the double-blind period (and corresponding 95% CI) from ANCOVA analysis.


Secondary
	
To evaluate the effect of ensifentrine on COPD symptoms.
	
Patients with moderate to severe COPD aged 40-80 years (inclusive) that are in the mITT population. See full list of inclusion and exclusion criteria in sections 5.1, 5.2 and 5.3 of study protocol.
	
Change from baseline (i.e. mean over the last 7 days of run-in) to the mean weekly value at Week 24 in COPD symptoms, as measured by daily diary (Evaluating Respiratory Symptoms for COPD [E-RS™;COPD])
	
Regardless of whether the patient discontinues treatment prematurely and regardless of major protocol deviation, as per the Treatment Policy strategy.
	
Estimated treatment difference at the end of the double-blind period (and corresponding 95% CI) from ANCOVA analysis.

Secondary
	
To evaluate the effect of ensifentrine on health-related quality of life.
	
Patients with moderate to severe COPD aged 40-80 years (inclusive) that are in the mITT population. See full list of inclusion and exclusion criteria in sections 5.1, 5.2 and 5.3 of study protocol.
	
1. Change from baseline in the St. George's Respiratory Questionnaire (SGRQ) total score at Week 24 2. Proportion of SGRQ responders at Week 24
	
Regardless of whether the patient discontinues treatment prematurely and regardless of major protocol deviation, as per the Treatment Policy strategy.
	
1. Estimated treatment difference at the end of the double-blind period (and corresponding 95% CI) from ANCOVA analysis. 2. Odds ratio for proportion of responders with an improvement of at least 4 units at the end of the double-blind period (and corresponding 95% CI) from logistic

[figure not shown]
						regression analysis.
--	--	--	--	--	--	----------------------

